5.9.4. WITHDRAWAL

In accordance with the legal requirements and ICH-GCP guidelines, a subject can leave the study at any time without having disadvantages. The subject may be withdrawn from the study at any time at the discretion of the investigator. The reason(s) for withdrawal shall be reported. Routine management and standard practice of care will continue for such a patient. Where a patient is withdrawn or excluded, the

**LUMINIZE_CLINICAL PROTOCOL**Document ID: VER-DOC-527
Controlled Document: VER-SIGN-3084TEMPLATE:
ONEPROJECTS/SIGN-267

Version: 4.0

Project: VERAFYE (VER)
Date: 22-Nov-2024 14:16:10
Page: 23 / 51

patient's number shall not be re-assigned to another subject. Data collected up to the point of subject withdrawal may be used but additional data may no longer be collected after the point at which a subject has been withdrawn from the study or withdraws consent.

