5.9.2. SUBJECT CLASSIFICATION

- Enrolled subject- Any participant who signs the informed consent form.
- Screen Failure subject- Any participant who signs the consent form but is found to not meet eligibility criteria.
- Intent subject- Any participant who signs the consent form, met the eligibility criteria but did not have the VERAFEYE Imaging Catheter inserted into the body.
- Attempt subject- Any participant who signs the consent form, met the eligibility criteria, did have the VERAFEYE Imaging Catheter inserted into the body but did not undergo the ablation/LAA/ASD closure procedure per this study protocol.
- Procedure subject - Any participant who undergoes the ablation/LAA/ASD closure procedure with the VERAFEYE System as imaging system per this study protocol.

These subjects are followed in accordance with the Follow-Up schedule and data will be included in all study analyses.

[figure not shown]
- Withdrawn subject - A participant who chooses to or is withdrawn from the study.
- Lost-to-follow up subject - A participant who cannot be reached anymore after 3 attempts.

Enrolment will be considered as complete when 20 procedure subjects have been enrolled.

The Figure below shows the subject classifications.

**LUMINIZE_CLINICAL PROTOCOL**Document ID: VER-DOC-527
Controlled Document: VER-SIGN-3084TEMPLATE:
ONEPROJECTS/SIGN-267

Version: 4.0

Project: VERAFYE (VER)
Date: 22-Nov-2024 14:16:10
Page: 22 / 51**Figure 5: Subject Classifications****5.9.3. END OF STUDY**

Individual study subject participation will end when the last subject follow-up visit is completed; when the subject withdrew or was withdrawn from the study or when the subject is considered as lost-to-follow up.

The study will be considered as complete when the last subject's follow up visit occurs or when subjects are no longer being considered for participation. Routine management and standard practice of care will continue for the subjects who have completed the study.

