5.10.4. POST-PROCEDURE VISIT

The Post-Procedure visit is applicable for attempt subjects and procedure subjects.

The post-procedure visit will occur per standard of care but not to exceed 2 days from the end of the study procedure. The data collection requirements of the post procedure visit are outlined below:

- Date of visit
- Physical assessment (incl. vital signs and 12-lead ECG)
- Changes in Medications Regimen

**LUMINIZE_CLINICAL PROTOCOL**Document ID: VER-DOC-527
Controlled Document: VER-SIGN-3084TEMPLATE:
ONEPROJECTS/SIGN-267

Version: 4.0

Project: VERAFYE (VER)
Date: 22-Nov-2024 14:16:10
Page: 28 / 51

- Adverse Events, if applicable
- Protocol Deviations, if applicable

5.10.5. 7-DAY FOLLOW-UP

The 7-day follow-up is applicable for attempt subjects and procedure subjects.

If the patient was discharged prior to the day 7 follow-up, a telephone contact will occur. If the patient is still hospitalized at the time of the day 7 follow-up, the 7 days follow-up will be performed as an in-hospital visit. The data collection at the day 7 follow-up includes:

- Date of contact (visit/telephone call)
- Changes in Medication Regimen
- Adverse Events, if applicable
- Protocol Deviations, if applicable

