5.13. SAFETY REPORTING**5.13.1. REPORTABLE EVENTS**

The investigator is responsible for documenting and reporting any of the following events to the study Sponsor:

- All Investigational Device Deficiencies
- All Serious Adverse Events
- Unanticipated Adverse Device Effects and Unanticipated Serious Adverse Device Effects
- All Thromboembolic Events
- All Device Related Adverse Events
- All Procedure Related Adverse Events
- New findings/updates in relation to already reported events

Definitions of reportable events are included in the Table below.

Table 6: Reportable Events Definitions

Term	Definition
Adverse Event	
Any untoward medical occurrence, unintended disease or injury, or any untoward clinical signs (including an abnormal laboratory finding) in subjects, users or other persons, in the context of a clinical investigation, whether or not related to the investigational medical device and whether anticipated or unanticipated.
 
NOTE 1: This includes events related to the investigational medical device or comparator.
 
NOTE 2: This definition includes events related to the procedures involved.

**LUMINIZE_CLINICAL PROTOCOL**Document ID: VER-DOC-527
Controlled Document: VER-SIGN-3084TEMPLATE:
ONEPROJECTS/SIGN-267

Version: 4.0

Project: VERAFYE (VER)
Date: 22-Nov-2024 14:16:10
Page: 35 / 51

Term	Definition
	
NOTE 3: For users or other persons, this definition is restricted to events related to the investigational medical device.

Adverse Device Effect	
Adverse event related to the use of an investigational medical device
 
NOTE 1: This includes any adverse event resulting from insufficiencies or inadequacies in the instructions for use, the deployment, the implantation, the installation, the operation, or any malfunction of the investigational medical device.
 
NOTE 2: This definition includes any event resulting from use error or from intentional misuse of the investigational medical device.
 
NOTE 3: This includes 'comparator' if the comparator is a medical device.

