5.13.2. REPORTING REQUIREMENTS**5.13.2.0.1. Investigator Reporting Requirements to Sponsor**

All reportable events experienced by study participants must be reported if they occur after the point of enrolment as defined in the subject classification section. Pre-existing conditions should not be reported as adverse events unless they worsen in severity or increase in frequency.

**LUMINIZE_CLINICAL PROTOCOL**Document ID: VER-DOC-527
Controlled Document: VER-SIGN-3084TEMPLATE:
ONEPROJECTS/SIGN-267

Version: 4.0

Project: VERAFYE (VER)
Date: 22-Nov-2024 14:16:10
Page: 37 / 51

Adverse events and device deficiencies must always be reported to the Sponsor through the CRFs. Completed CRFs are to be sent to the following email address of the sponsor:

[contact]

Reporting timelines are included in Table 7 below.

Table 7: Investigator Reporting Requirements

Event Classification	Communication Method	Communication Timeline pre-market studies
Unanticipated Adverse Device Effect / Unanticipated Serious Adverse Device Effect	Complete AE CRF page with all available new and updated information.	
Within 1 business day of first becoming aware of the event.Terminating at the end of the study
	Provide all relevant source documentation (de-identified/pseudonymized) for reported event, as requested by sponsor.	
Upon request of sponsor.
Serious Adverse Event	Complete AE CRF page with all available new and updated information.	
Within 3 calendar days of first becoming aware of the event or as per local/regional regulations.Reporting required through the end of the study
	Provide all relevant source documentation (de-identified/pseudonymized) for reported event.	
Upon request of sponsor

**LUMINIZE_CLINICAL PROTOCOL**Document ID: VER-DOC-527
Controlled Document: VER-SIGN-3084TEMPLATE:
ONEPROJECTS/SIGN-267

Version: 4.0

Project: VERAFYE (VER)
Date: 22-Nov-2024 14:16:10
Page: 38 / 51

Event Classification	Communication Method	Communication Timeline pre-market studies
Serious Adverse Device Effects	Complete AE CRF page with all available new and updated information.	
Within 3 calendar days of first becoming aware of the event or as per local/regional regulations.Reporting required through the end of the study

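### Section 5.9.2 closes enrolment at 20 procedure subjects against 40 elsewhere; 5.9.4 also bars safety data after investigator withdrawal, and 5.12 and 5.9.3 need clearer timing

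*Combined protocol and SAP*

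**What the plan says.** **Enrolment number.** The synopsis, 5.7 and 5.9.1 all set completion of enrolment at 40 subjects who have had the procedure. 5.7 adds that revision 4.0 raised the number from 20, to gain more data and cover more operators. 5.9.1 refers to the subject classification section for the definition. That section, 5.9.2, ends by closing enrolment at 20 procedure subjects.

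**Withdrawal.** 5.9.4 gives the investigator a free hand: "The subject may be withdrawn from the study at any time at the discretion of the investigator". It then provides that "additional data may no longer be collected after the point at which a subject has been withdrawn from the study or withdraws consent". 5.9.3 ends individual participation, among other cases, "when the subject withdrew or was withdrawn from the study".

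Other sections point the other way:
- 5.10.4: "The Post-Procedure visit is applicable for attempt subjects and procedure subjects".
- 5.10.5: "The 7-day follow-up is applicable for attempt subjects and procedure subjects".
- 5.13.2: "All reportable events experienced by study participants must be reported if they occur after the point of enrolment".
- 5.13.1 lists among the reportable items "New findings/updates in relation to already reported events".
- 5.9.2 defines a withdrawn subject as "A participant who chooses to or is withdrawn from the study", so the term used in 5.13.2 still covers that person.

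**Timing.** 5.12 places the clinical study report at the close of enrolment. The synopsis puts that close at the 40th completed procedure, and its schedule puts the last contact at day 7 ± 2. 5.9.3 gives two alternative ends of study: the last follow-up visit, or the point at which nobody further is being considered for entry. Table 7 in 5.13.2 runs serious event reporting to the end of the study.

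**The concern.** The enrolment figure is the main point. A site or monitor who follows the cross-reference in 5.9.1 arrives at the one section that gives a different number, and that number would end enrolment at half the planned size. This would defeat the reason 5.7 gives for the increase.

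The withdrawal rule matters because this is a pilot-stage study of an investigational catheter, and 5.14.10 allows severe device-related complications in even one subject to justify ending it. The later course of a single event can therefore count. Under 5.9.4, an exposed subject whom the investigator withdraws, and who has not withdrawn consent, drops out of adverse event collection for the rest of the 7 days. The sections on visits and reporting suggest that collection should go on, and the protocol does not say which rule governs.

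The timing sentences raise a smaller question: whether the report, or the reporting period, could close with a safety contact still due.

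**Working it through.** **1. Enrolment number.** There is no sample size calculation to reproduce. 5.7 says the size has no statistical basis, 5.6 plans no hypothesis test, and no alpha, power or effect size is given. The check is a comparison of stated figures:

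| Place | Procedure subjects at which enrolment closes |
|---|---|
| Synopsis | 40 |
| 5.7 | 40 (raised from 20) |
| 5.9.1 | 40, with reference to subject classification |
| 5.9.2 Subject classification | 20 |

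Difference: 40 − 20 = 20 subjects, and 20/40 = 50% of the target.

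To illustrate the information at stake, take a type of event that is never observed. The exact two-sided 95% upper limit is 1 − 0.025^(1/n):
- n = 20: 1 − 0.025^(1/20) = 16.8%
- n = 40: 1 − 0.025^(1/40) = 8.8%

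The chance of seeing at least one event is 1 − (1 − p)^n. The documents give no rate, so p is assumed:
- p = 1%: 18.2% at n = 20, 33.1% at n = 40
- p = 10%: 87.8% at n = 20, 98.5% at n = 40

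**2. Withdrawal.** Take an attempt or procedure subject whom the investigator withdraws on Day 0 after the catheter has been inserted.
- Under 5.9.3 participation ends, and under 5.9.4 nothing more is collected. Both remaining adverse event assessments are lost: the post-procedure visit (Day 0 to 2) and the day-7 contact. If withdrawal comes after the post-procedure visit, only the day-7 contact is lost.
- Under 5.10.4 and 5.10.5 the subject belongs to a class that receives both contacts.
- Under 5.13.2 events after enrolment must be reported, and under 5.13.1 so must updates to events already reported.

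The two sets of rules give different answers for this subject. The event that prompts withdrawal is still captured, because 5.9.4 requires the reason and 5.15.4 requires the condition at withdrawal. What remains exposed is that event's later course and any new event up to day 7. No rate can be computed from the documents.

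**3. Timing.** If the report is cut at the 40th procedure, the 40th subject's day-7 contact is always outstanding. Any larger count needs an accrual assumption. With even spacing, gap = T/39 and a month of 30.44 days, count the subjects whose procedure was fewer than w days before the 40th (the 40th included), for w = 5, 7 and 9:
- T = 6 months (182.6 days, gap 4.68): 2, 2, 2
- T = 5 months, assumed (152.2 days, gap 3.90): 2, 2, 3
- T = 7 months, assumed (213.1 days, gap 5.46): 1, 2, 2

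These counts are illustrative only, because 5.7 has the sites working one after the other, which makes even spacing doubtful.

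Room in the plan: (7 − 6) × 30.44 − 9 = 21.4 days between the latest permitted last contact and the planned end, taking the approximate 6 and 7 months at face value.

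**The case against.** On the enrolment number, three places say 40 and 5.7 explains the change, so someone who reads the whole protocol is unlikely to stop at 20. That lowers the risk. It does not remove a contradiction within the current text.

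On withdrawal, the best defence is that 5.9.3 and 5.9.4 agree with each other: participation ends, so collection ends, and 5.10.4 and 5.10.5 only name the classes that receive the visits. It can also be said that resting on the word participant in 5.13.2 proves too much, since 5.9.2 uses it of screen failures as well. That second argument fails, because 5.13.2 does cover everyone from consent onwards. The first leaves the conflict with 5.13.1 and 5.13.2 in place.

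Two parts of the objection do stand. The only specific withdrawal trigger described is a thrombus, under pre-procedural imaging in 5.10.3.3, where the procedure is aborted and the catheter would normally not have been inserted. So the documents describe no route by which an exposed subject comes to be withdrawn. And continued collection depends on what subjects consented to, which cannot be checked from the public text.

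On timing, the objection largely succeeds. 5.9.2 says procedure subjects are followed to schedule and their data enter all analyses, 5.9.1 makes the 7-day contact the last required one, and 5.12 stops no data collection.

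**Conclusion.** The enrolment figure in 5.9.2 is wrong as written, and should be corrected: 20 against 40, half the target. It is probably a remnant. A reader might infer that the study is meant to stop early at 20; the synopsis, 5.7 and 5.9.1 do not support that. The upper limits of 16.8% and 8.8% show only the information lost, since the size was not chosen on statistical grounds.

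The withdrawal conflict is also real and cheap to settle. Its expected effect is small: likely rare cases, each losing one or two adverse event assessments. A reader might infer that safety data will be lost as a matter of routine, or that stopping collection when consent is withdrawn is itself a fault. The documents support neither: the prompting event is recorded, and stopping at withdrawal of consent is ordinary practice.

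The timing point is minor. A reader might infer that the report is planned without day-7 data, or that event reporting will close before the last contact. The inclusion rule in 5.9.2 and the total of about 7 months show that this is not intended. Only the 40th subject's outstanding contact is certain on a literal reading; the range of 1 to 3 of 40 rests on even accrual over an assumed 5 to 7 months and is not a bound.

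**What to change.** 1. In 5.9.2, replace 20 with the 40 stated in the synopsis, 5.7 and 5.9.1. This costs nothing beyond the edit, as 40 is already the plan.
2. In 5.9.4, limit the bar on further data to withdrawal of consent, so that adverse events and updates to reported events are still collected to day 7 in exposed subjects withdrawn by the investigator, subject to consent form wording. Align 5.9.3 and 5.13.2. The cost is about one phone contact per such subject, plus consent form wording where needed.
3. In 5.12, time the report after the last subject's day-7 contact. In 5.9.3, remove or qualify the second end-of-study alternative, so that event reporting also runs past that contact. No study time is added: the last contact falls at most 9 days after the 40th procedure, within the planned 7 months.

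All three can go into one amendment, which needs ethics committee approval and, as applicable, regulatory authority approval under 5.14.9.

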5.9.5. LOST-TO-FOLLOW UP

Before a participant is deemed lost to follow-up, the investigator or designee will make every effort to regain contact with the participant (where possible, 3 telephone calls and, if necessary, a letter to the participant's last known mailing address or local equivalent methods). These contact attempts should be documented in the participant's medical record or study file. Should the participant continue to be unreachable, he or she will be considered as lost to follow-up.

5.10. STUDY ASSESSMENTS**5.10.1. INFORMED CONSENT**

If a potential participant is found to be eligible for enrolment, the study consent form will be reviewed with the subject and the study methods and requirements will be explained. Subjects will be provided with sufficient information to make an informed decision about their participation in this study. Subjects will be given sufficient time to consider participation and ask questions if necessary.

No study-specific procedures should be conducted prior to consent. A copy of the signed consent form will be provided to the study participant and the original signed consent form will be maintained in the subject's files at the site. The consent form must be signed by the subject, and the Investigator-designated research professional obtaining the consent.

All changes to the consent form shall require EC approval; a determination will be made by the sponsor regarding whether a new consent needs to be obtained from participants who provided consent, using a previously approved consent form.

The patients who have received the study patient information for consideration of participation in the study will be listed in a screening log, regardless of whether they are eligible to the study or whether they consented to participate or not. The screening log list will not include the patient identity information except for the first and the second name initials, and the date of providing the study written patient information to the patient.

5.10.2. BASELINE VISIT

The data collection requirements for the baseline visit are outlined below and will be collected prior to the procedure.

- Verification of eligibility criteria
- Documentation of informed consent process, including ICF signature date (see section 13.1.1 below)
- Subject demographics, including age, gender and race

**LUMINIZE_CLINICAL PROTOCOL**Document ID: VER-DOC-527
Controlled Document: VER-SIGN-3084TEMPLATE:
ONEPROJECTS/SIGN-267

Version: 4.0

Project: VERAFEYE (VER)
Date: 22-Nov-2024 14:16:10
Page: 24 / 51

- Medical history, including cardiac history and arrhythmia disorder history
- Physical assessment (including height, weight, blood pressure, heart rate, 12-lead ECG))
- Pre-procedural imaging per hospital's standard of care, if performed at baseline*
- Medication Regimen
- Adverse events, if applicable
- Protocol deviations, if applicable

*Pre-procedural imaging data will be saved and stored to external media, as provided by the sponsor

5.10.3. PROCEDURE

5.10.3.1. General

The procedure visit must occur within 60 calendar days of the baseline visit.

The ablation, or LAA/ASD closure procedure must be performed by investigators trained in Electrophysiology or Interventional Cardiology, trained to the LUMINIZE study protocol and authorized by LUMA Vision to handle investigational devices. Up to 4 operators per site will be allowed to perform study procedures, unless written approval from LUMA Vision was obtained.

5.10.3.2. VERAFEYE System Preparation/LUMA Vision Support

The System Console will create a record for each view attempted. In order to accurately capture information

relevant to the study, the following steps need to be followed for each procedure:

1. Start a new study. Input subject name, date of birth, gender and subject ID
2. In Graphical User Interface (GUI) main screen, select appropriate 2D and 4D configs.
3. In the Component screen,
 - Home the motor (if the button is enabled).
 - Input the VERAFEYE Imaging Catheter serial number with the format.
 - Confirm the VERAFEYE Imaging Catheter has been flushed and confirm the connection.
4. If tracking sensors are disconnected,
 - Disable tracking from the tracking tab before inserting the sensor to the control unit.
 - Enable tracking again after connecting the sensor.
5. Start imaging.
6. Navigate to intended view (see section 12.6), manipulating 3D volume and 2D plane as required.
7. Acquire clip and full data.
8. Freeze if needed for measurements / change configurations and repeat acquisition.
9. Navigate to the next intended view (see section 12.6).

**LUMINIZE_CLINICAL PROTOCOL**Document ID: VER-DOC-527
Controlled Document: VER-SIGN-3084TEMPLATE:
ONEPROJECTS/SIGN-267

Version: 4.0

Project: VERAFEYE (VER)
Date: 22-Nov-2024 14:16:10
Page: 25 / 51

10. Before finishing a study, always freeze the imaging and wait until the motor stops. Then, select the "finish" option in the dropdown with the subject name. Close the study and the data will automatically save.

LUMA Vision will ensure (a) company representative(s) is/are present during each procedure to manage the System Console and to assist the physician with the VERAFEYE Imaging Catheter preparation.

5.10.3.3. Procedure Workflows**Pre-Procedural Imaging**

Pre-procedural imaging will be performed per hospital standard of care to assess the anatomy and to exclude the presence of thrombus. If an intracardiac thrombus is visualized, the procedure will be aborted and the subject will be withdrawn from the study. Pre-procedural imaging may be collected at baseline or on the day of the procedure.

Intra-Procedural Imaging

VERAFEYE imaging data from the right atrium will be obtained during the ablation, or LAA/ASD closure procedure. This procedure is to be performed using a commercially available ablation catheter or LAA/ASD closure device. The choice of the ablation catheter, or LAA/ASD closure device is at the operator's discretion. This ablation, or LAA/ASD closure procedure will be performed according to standard of care. The ablation, or LAA/ASD closure procedure will not be guided by the data collected from the VERAFEYE System, the physician is to adhere to a standard workflow and rely on standard imaging and diagnostic tools, as applicable. In order to prevent artifact between the VERAFEYE System and the standard of care echocardiography imaging (intracardiac echocardiography (ICE) transesophageal echocardiography (TEE)), the VERAFEYE imaging has to be frozen during standard of care echocardiography imaging and vice versa.

No concomitant procedures are allowed to be performed at the time of the ablation, or LAA/ASD closure procedure under this protocol. It is also not allowed to combine an ablation procedure with an LAA/ASD closure procedure or to combine an LAA closure procedure with an ASD closure procedure.

It is recommended that the following views with the VERAFEYE Imaging Catheter be obtained in order to visualize the major anatomical structures, as well as third party devices.

RA (typical AFL) Ablation

- Home view
- A variety of anatomical views from different VERAFEYE Imaging Catheter locations, at the discretion of the investigator
- View to visualize mapping* and/or ablation catheter

*If used, per hospital standard's of care

**LUMINIZE_CLINICAL PROTOCOL**Document ID: VER-DOC-527
Controlled Document: VER-SIGN-3084TEMPLATE:
ONEPROJECTS/SIGN-267

Version: 4.0

Project: VERAFYE (VER)
Date: 22-Nov-2024 14:16:10
Page: 26 / 51**LA (AF) Ablation**

- Home view
- A variety of anatomical views from different VERAFYE Imaging Catheter locations, at the discretion of the investigator
- Transseptal puncture view
- View to visualize mapping* and/or ablation catheters

If used, per hospital standard's of care*LAA Closure**

- Home view
- A variety of anatomical views from different VERAFYE Imaging Catheter locations, at the discretion of the investigator
- Transseptal puncture view
- View to visualize closure device delivery catheter

ASD Closure

- Home view
- A variety of anatomical views from different VERAFYE Imaging Catheter locations, at the discretion of the investigator
- View to visualize closure device delivery catheter

Indications for conversion to general anesthesia are at the discretion of the treating physicians and include, but are not limited to, hemodynamic instability, inability to maintain a protected airway during the procedure and patient discomfort. Routine clinical assessment for complications will be made during the case.

The VERAFYE Imaging Catheter is to be removed after the removal of any third party catheters.

Post-Procedural Imaging

VERAFYE imaging data will be collected after the last ablation has been performed/after deployment of the closure device. Prior to the completion of the procedure (after removing all the devices except the VIC), additional VERAFYE imaging of the pericardial space maybe performed at the discretion of the physician.

